2.4 Rationale

Revlimid® (lenalidomide) is indicated for the treatment of patients with transfusion-dependent anemia due to Low- or Intermediate-1-risk myelodysplastic syndromes associated with a deletion

CONFIDENTIAL

This document is confidential. Do not disclose or use except as authorized.

5q cytogenetic abnormality with or without additional cytogenetic abnormalities. Revlimid® is also approved in combination with dexamethasone for the treatment of patients with multiple myeloma and Revlimid® has recently been approved in the treatment of patients with mantle cell lymphoma whose disease has relapsed or progressed after two prior therapies, one of which included bortezomib.

2.4.1 Role of Lenalidomide in Acute Myeloid Leukemia

Recently, lenalidomide has been shown to have activity in acute myelogenous leukemia, given at a dose of 35-50 mg daily as a single agent. (42-44) Chandler and colleagues performed a dose escalation trial of lenalidomide. The 50 mg dose was the maximum tolerated dose with higher doses resulting in dose-limiting fatigue. (42) Blum et al reported on a Phase I study of 31 patients with relapsed or refractory AML who received lenalidomide in doses of 25-75 mg daily Days 1-21 of a 28 day cycle. (43) Fatigue was considerable at a dose of 75 mg. Five patients achieved a complete response.

Thirty-three patients over age 60 received lenalidomide 50 mg daily in 2 28 day cycles, followed by a low dose lenalidomide (10 mg) maintenance if they did not progress. Overall complete remission/complete remission with incomplete platelet recovery rate was 30%, with patients with low blast counts more likely to respond. (44) The CR rate was 53% in patients completing the high dose lenalidomide treatment. The median time to CR was 30 days and the duration of CR was 10 months. The most common toxicities were neutropenia, thrombocytopenia, and infection.

Two patients with AML with trisomy 13 cytogenetic abnormality responded to lenalidomide. (45) One patient received lenalidomide 50 mg daily for 14 days, followed by 30 days off therapy and 21 days of lenalidomide 50 mg daily, and the other patient received a dose of 35 mg daily Days 1-21 of repeated 28 day cycles. Both patients achieved a complete remission, and relapsed after 9 months of CR.

Sekeres and colleagues treated 37 older AML patients with del (5q) with lenalidomide 50 mg daily for induction, and 10 mg daily for maintenance. (46) The median age was 74 years. Fourteen patients completed induction, and five patients achieved a complete remission.

Combinations of lenalidomide with standard chemotherapy are currently under investigation.

Laboratory correlates of the AML patients treated with lenalidomide indicated suppression of the tumor clone, as assessed by fluorescence in situ hybridization for del (5q31). (47) Twenty-eight patients with AML or high risk MDS, all with chromosome 5 abnormalities, alone or in combination, were treated with lenalidomide 30 mg daily for 16 weeks. Nineteen percent of patients had a major cytogenetic response and eight percent had a minor cytogenetic response. Thirty-five percent of patients had a clinical response, including 9 of 10 who completed the full 16 weeks of treatment.

Data from Ohio State University and others has shown that microRNA (miR)-181 a and b is associated with improved outcomes in cytogenetically normal and cytogenetically abnormal AML. (48,49) More recent work suggests that lenalidomide increases miR-181a and b, which

may contribute to improved outcomes, and is consistent with pretreating patients with lenalidomide prior to induction chemotherapy. (50)

Lenalidomide has also been used to treat relapse after allogeneic stem cell transplant for AML; lenalidomide was given at a dose of 10 mg daily and CR was achieved. (51)

Recent data suggests lenalidomide may affect clonal architecture in patients with myelodysplasia. (52) Loss of treatment efficacy coincided with re-expansion of the dominant subclone.

A Phase I study (07-006) of lenalidomide and bortezomib for patients with MDS and AML has been completed at Massachusetts General Hospital and Dana Farber Cancer Institute. (53) Lenalidomide was given at a dose of 10 mg daily, Days 1-21 of 28 days cycles. The drug was tolerated well. 23 patients (14 men) were enrolled; one patient was inevaluable due to disease progression prior to starting protocol therapy. The median age was 73 years (range 54-87). There was 1 DLT observed, neutropenia, in 6 patients treated with 1.0 mg/m^2 bortezomib and no DLTs at 0.7 or 1.3 mg/m^2 . The median number of cycles was 2 (range 2-9). Grade ≥ 3 toxicities possibly attributable to the treatment at any dose level were: anemia (2), thrombocytopenia (10), leukopenia (3), infection (1), rash (2), dyspnea (1), dizziness (1), hypotension (1), pneumonia (2) and neuropathy (1). Among the 14 patients with MDS, 1 patient with RARS experienced a CR and 2 with RAEB-2 experienced marrow CR (mCR). Among the 8 patients with AML, there was 1 CR.

Protocol 12-202, Phase I study of Lenalidomide plus mitoxantrone, etoposide, and cytarabine for patients with relapsed and refractory AML has just been completed at DF/HCC. Results were presented in abstract form at the American Society of Hematology, December 2015. (54)

The primary objective of this Phase I trial was to evaluate the safety of lenalidomide in combination with MEC for relapsed acute myelogenous leukemia and determine a safe Phase II dose and schedule. The secondary objectives included time to neutrophil (>500) and platelet recovery ($> 20K$), the complete response rate with and without platelet recovery, and the treatment-related mortality within the first 45 days. Patients received lenalidomide in escalating doses at dose levels: 5 mg, 10 mg, 25 mg and 50 mg. Lenalidomide was given initially Days 1-14, and then due to neutropenia was decreased to Days 1-10. The chemotherapy was given as follows: Mitoxantrone $8 \text{ mg/m}^2/\text{day}$ Days 4-8, Etoposide $100 \text{ mg/m}^2/\text{day}$ Days 4-8, and Cytarabine $1000 \text{ mg/m}^2/\text{day}$ Days 4-8. Thirty-six patients were enrolled with a median age of 61 years. Forty-five percent of patients had received 2 or more prior chemotherapy regimens, and 22% had received a prior stem cell transplant. Thirteen patients entered complete remission and one patient had complete remission with incomplete count recovery for a response rate of 39%. The median time to ANC > 500 was 30 days and the median time to platelet recovery $> 20,000$ was 34 days. Two of 6 patients treated with lenalidomide for 14 days had no count recovery at Day 42. After the dose adjust to 10 days, only 1 of 13 patients at lenalidomide 50 mg daily x 10 days had prolonged count recovery. Thus, the recommended phase 2 dose is 50 mg daily for 10 days. There were 4 deaths on study, deemed unrelated to study drug. One patient died of sepsis, one of infection, and two of respiratory failure.

We propose to study the efficacy of lenalidomide and MEC chemotherapy as reinduction treatment in patients with relapsed and refractory AML. The survival is poor for patients with relapsed or refractory leukemia treated with standard chemotherapy. Lenalidomide has been demonstrated to have significant activity in AML. Our Phase I study demonstrated that lenalidomide in combination with MEC chemotherapy will be safely tolerated. Patients with relapsed and refractory AML will be eligible for this study. If this combination proves to be effective, a multicenter Phase III study would be considered.

2.5 Correlative Studies Background

Acute myeloid leukemia (AML) is a disease characterized by the combinatorial action of multiple somatic mutations that lead to an arrest in normal hematopoietic differentiation and uncontrolled growth of immature bone marrow myeloid blasts. (55, 56)

Advances in gene sequencing technology over the past decade have allowed for the identification of over 50 recurrent mutations in AML patients. Mutational testing of a limited number of genes is already considered an integral part of standard clinical practice. The presence of mutations in *FLT3* and *NPM1* help define prognosis and determine treatment algorithms. Recent clinical trial data have demonstrated the clinical efficacy of the tyrosine kinase inhibitor midostaurin in the presence of a *FLT3* mutation. AML patients with *IDH* mutations are now being enrolled in clinical trials utilizing small molecule inhibitors of this mutant enzyme (57). Some mutations may also predict response or resistance to certain therapeutic interventions. In myelodysplasia, a related myeloid disease, the finding of isolated deletion of 5q is already an approved indication for the use of lenalidomide (58). However, concomitant mutations in *TP53* have been demonstrated to predict a poor response to treatment with lenalidomide in these patients (59). Whether this observation holds true in AML remains an open question. Identifying genetic markers that predict response to specific agents so that we can triage patients appropriately is an important and unmet clinical need.

We now routinely perform DNA sequencing of recurrently mutated genes from clinical samples using next generation sequencing assays, including the Rapid Heme Panel or the Heme SNaPshot assay. These assays provide targeted next-generation sequencing of recurrently mutated genes as well as high-resolution genomic copy number data at these loci. Mutation and copy number status will be determined. With this genetic information we can classify patients into molecularly defined groups; for instance, *de novo* AML, secondary AML and *TP53* associated AML (60). We can also look for correlations between specific genetic lesions and response to therapy in this clinical trial. In doing this, we hope to identify specific factors associated with response and primary resistance to lenalidomide in AML.

3. PARTICIPANT SELECTION

3.1 Eligibility Criteria

Participants must meet the following criteria on screening examination to be eligible to participate in the study. All required tests must be performed within 21 days of the start of treatment.

CONFIDENTIAL

This document is confidential. Do not disclose or use except as authorized.

3.1.1 Acute myelogenous leukemia diagnosed by WHO criteria with one of the following (patients with biphenotypic leukemia are eligible, provided that the treating physician determines an AML treatment regimen is appropriate)

- Primary refractory disease following ≥ 1 cycle of induction chemotherapy
- First relapse or higher. Patients with primary or secondary acute myelogenous leukemia are eligible.

3.1.2 Age 18-70 years old

3.1.3 LVEF ≥ 50 %

3.1.4 ECOG Performance status 0-2

3.1.5 Able to adhere to study schedule and other protocol requirements.

3.1.6 Participants must have normal organ function as defined below, unless felt due to underlying disease and approved by the overall PI. Patients with Gilbert's disease may have total bilirubin up to ≤ 3 x institutional ULN.

- Creatinine < 2.0 mg/dL, and eGFR ≥ 60 mL/min
- Total bilirubin ≤ 1.5 x institutional ULN
- AST (SGOT) and ALT (SGPT) ≤ 3 x institutional ULN

3.1.7 Patients may receive hydroxyurea, steroids, or leukapheresis as necessary until Day 5 of treatment.

3.1.8 Patients must give voluntary written informed consent and HIPAA authorization before performance of any study-related procedure not part of normal medical care, with the understanding that consent may be withdrawn by the subject at any time without prejudice to future medical care.

3.1.9 Patients may have had prior treatment for MDS or AML, including prior lenalidomide for MDS or AML or another condition.

3.1.10 Patient may have had prior autologous or allogeneic transplant (family member, unrelated donor, or cord blood) if there is at least 90 days between transplant and study entry.

3.1.11 Patients may also have had donor lymphocyte infusion if there is at least 60 days between donor lymphocyte infusion and study entry.

3.1.12 Patients on immunosuppression are also eligible.

3.1.13 Females of childbearing potential (FCBP)[†] must have a negative serum or urine pregnancy test with a sensitivity of at least 50 mIU/mL prior to receiving treatment with lenalidomide, and must either commit to continued abstinence from heterosexual intercourse or begin TWO acceptable methods of birth control, one highly effective method and one additional effective method AT THE SAME TIME, at least 28 days before she starts taking lenalidomide. FCBP must also agree to ongoing pregnancy testing. Men must agree to use a latex condom during sexual contact with a FCBP even if they have had a successful vasectomy.

3.1.14 Ability to understand and the willingness to sign a written informed consent document.

3.1.15 All study participants must be registered into the mandatory Revlimid REMS ® program, and be willing and able to comply with the requirements of the REMS ® program. Females of reproductive potential must adhere to the scheduled pregnancy testing as required in the Revlimid REMS® program.

[†] A female of childbearing potential is a sexually mature female who: 1) has not undergone a hysterectomy or bilateral oophorectomy; or 2) has not been naturally postmenopausal for at least 24 consecutive months (i.e., has had menses at any time in the preceding 24 consecutive months)

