Simon's two stage optimal design is used to compute the sample size. A total number of 40 patients is needed in order to detect a 20% CR rate increase assuming the CR for null hypothesis is 25% with a 90% power and 9% type I error. The study will be reevaluated if 4 or fewer responses out of 18 patients are observed and the study will be declared inactive if fewer than 14 responses are seen in the total 40 patients. The probability of stopping at the first stage is 0.52.

Accrual Objective: 40 - 42 patients in order to enroll 40 evaluable patients.

Accrual Period: The estimated accrual period is 2.5 years

Eligibility Criteria:

The following criteria must be met prior to enrolling.

- Acute myelogenous leukemia diagnosed by WHO criteria with one of the following:
 - Primary refractory disease following ≥ 1 cycle of induction chemotherapy.

CONFIDENTIAL

This document is confidential. Do not disclose or use except as authorized.

- First relapse or higher. Patients with primary or secondary acute myelogenous leukemia are eligible. Patients with biphenotypic leukemia are eligible.
- 18-70 years
- LVEF \geq 50%
- ECOG Performance status 0-2
- Creatinine < 2.0 mg/dl and eGFR ≥ 60 mL/min.
- Total bilirubin $< 1.5 \times$ institutional ULN
- AST (SGOT) and ALT (SGPT) $\leq 3 \times$ institutional ULN
- Able to adhere to study schedule and other protocol requirements
- Patients may receive hydroxyurea, steroids, or leukapheresis as necessary until Day 5 of treatment.

Treatment Description:

Patients will receive only one cycle of treatment, as below:

1. Lenalidomide Days 1-10
2. Mitoxantrone by IV infusion over approximately 6-10 minutes for 5 days (days 4-8)
3. Etoposide IV over approximately 1 hour daily for 5 days (days 4-8)
4. Cytarabine IV over approximately 1 hour daily for 5 days (days 4-8).

	Day 1	Day 2	Day 3	Day 4	Day 5	Day 6	Day 7	Day 8	Day 9	Day 10
Mitoxantrone (intravenous)				X	X	X	X	X		
Etoposide (intravenous)				X	X	X	X	X		
Cytarabine (intravenous)				X	X	X	X	X		
Lenalidomide (oral)	X	X	X	X	X	X	X	X	X	X

Study Duration:

Participants will be followed for at least 50 days after the start of protocol treatment.

Participants will be followed for relapse and survival at 3 months after treatment, and then every six months until 3 years from start of treatment. Patients removed from the study treatment will continue to be followed for relapse and survival for up to three years following initiation of study treatment

CONFIDENTIAL

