3.2 Exclusion Criteria

- 3.2.1 Known hypersensitivity to thalidomide or lenalidomide (if applicable).
- 3.2.2 The development of erythema nodosum if characterized by a desquamating rash while taking thalidomide or similar drugs.
- 3.2.3 Known seropositive for human immunodeficiency virus (HIV). HIV testing is not required. Hepatitis testing is not required.
- 3.2.4 Patients who have had a myocardial infarction within 6 months of enrollment or has New York Heart Association (NYHA) Class III or IV heart failure, uncontrolled angina, uncontrolled ventricular arrhythmias, or electrocardiographic evidence of acute ischemia or active conduction system abnormalities.
- 3.2.5 Any serious medical condition laboratory abnormality or psychiatric illness that would prevent the subject from signing the consent form.
- 3.2.6 Any condition, including laboratory abnormalities, that in the opinion of the investigator places the subject at unacceptable risk if he/she were to participate in the study or confounds the ability to interpret data from the study.
- 3.2.7 Patients with major surgery within 28 days prior to treatment.
- 3.2.8 Patients with any serious medical or psychiatric illness that could, in the investigator's opinion, potentially interfere with the completion of treatment according to this protocol.
- 3.2.9 Patient has received an investigational agent or cytotoxic chemotherapy (excluding hydroxyurea) within 7 days of study entry. If an LP is performed for clinical care, intrathecal chemotherapy (although not systemic chemotherapy) may be given as prophylaxis per institutional standard of care, but should be completed >24 hours prior to administration of protocol therapy.
- 3.2.10 Patients with acute promyelocytic leukemia.
- 3.2.11 Females who are pregnant

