5.3 Agent Administration

Treatment will be administered on an inpatient basis. Expected toxicities and potential risks for mitoxantrone, etoposide, cytarabine, and lenalidomide are outlined in Toxicities and Dosing Delays/Dose Modification (section 6).

Administer chemotherapeutic agents according to institutional policies and procedures. Lenalidomide should be administered prior to MEC each day. During the administration of MEC, mitoxantrone will be administered first, followed by etoposide, followed by cytarabine.

General dosing guidelines for lenalidomide are provided below. Please refer to the dosage and

CONFIDENTIAL

This document is confidential. Do not disclose or use except as authorized.

administration schedule specified in the prescribing information.

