5.3.1.4 Patients with Impaired Renal Function

Lenalidomide is primarily excreted unchanged by the kidney; for other approved indications, starting dose adjustment is recommended in patients with CKD. Based on a PK study in subjects with CKD due to nonmalignant conditions, lenalidomide starting dose adjustments are recommended for patients with $\text{CrCl} < 60 \text{ mL/min}$; therefore, patients must have a $\text{CrCl} \geq 60 \text{ mL/min}$ to be eligible for this study.

Because lenalidomide is primarily excreted unchanged by the kidney, monitoring of renal function is advised. No dose adjustments are required for patients with $\text{CrCl} \geq 60 \text{ mL/min}$. Patients must have eGFR of $\geq 60 \text{ mL/min}$ and $\text{Cr} < 2 \text{ mg/dL}$ to enroll on the study. Refer to Section 6.2, Table 4 for lenalidomide dose adjustment recommendations if patients develop worsened renal function while on treatment.

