Toxicity	Grade 1	Grade 2	Grade 3	Grade 4
Acute kidney injury	No change in dose	Decrease lenalidomide dose by one level according to Table 3.	Hold lenalidomide. If resolves to \leq grade 2, restart lenalidomide at next lower dose level and continue through the remainder of the scheduled treatment. Omitted doses are not made up.	Hold lenalidomide. If resolves to \leq grade 2, restart lenalidomide at next lower dose level and continue through the remainder of the scheduled treatment. Omitted doses are not made up.
Other clinically significant, non-hematologic toxicity thought to be related to lenalidomide	No change in dose	No change in dose	Hold lenalidomide. If resolves to \leq grade 2, restart lenalidomide at next lower dose level and continue through the remainder of the scheduled treatment. Omitted doses are not made up.	Hold lenalidomide. If resolves to \leq grade 2, restart lenalidomide at next lower dose level and continue through the remainder of the scheduled treatment. Omitted doses are not made up.

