3.7.3 Eligibility Exceptions

CTEP specifically prohibits registration of a participant on any NCI Sponsored protocol that does not fully and completely meet all eligibility requirements. No exceptions to the eligibility requirements for a protocol without DFCI IRB approval will be permitted. All Participating Institutions are required to fully comply with this requirement. The process for requesting an eligibility exception is defined below.

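### The organ-function waiver in 3.1.6 also covers the creatinine/eGFR limit, which 5.3.1.4 makes an unconditional enrolment requirement; limit the waiver to bilirubin and AST/ALT

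*Combined protocol and SAP*

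**What the plan says.** - **Section 3.1.6** asks for normal organ function, "unless felt due to underlying disease and approved by the overall PI". Three bullets follow: creatinine and eGFR, total bilirubin, and AST/ALT. The section has a separate allowance for bilirubin in Gilbert's disease. It makes no exception for the renal bullet.
- **Section 5.3.1.4** notes that lenalidomide leaves the body mainly unchanged through the kidney and that "lenalidomide starting dose adjustments are recommended for patients with" a creatinine clearance under 60 mL/min. From this it concludes that a clearance of at least 60 mL/min is needed for eligibility. It then repeats the requirement for enrolment as eGFR of at least 60 mL/min with creatinine below 2 mg/dL. Neither statement mentions a waiver. The section refers to Table 4 only "for lenalidomide dose adjustment recommendations if patients develop worsened renal function while on treatment".
- **Synopsis, Eligibility Criteria** lists "Creatinine < 2.0 mg/dl and eGFR ≥ 60 mL/min" and shows no waiver for any organ-function limit, liver or renal.
- **Tables 2 and 3** give one lenalidomide starting dose, 50 mg. In Table 4 the renal row is acute kidney injury. At grade 2 the instruction is "Decrease lenalidomide dose by one level according to Table 3". At grades 3 and 4 lenalidomide is held and, on recovery to grade 2 or less, restarted one level lower.

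**The concern.** The two sections give opposite answers for a patient whose reduced renal function is attributed to the leukemia. Under 3.1.6 the overall PI may admit the patient. Under 5.3.1.4 the patient cannot enrol. Registration works from the Section 3 criteria and an eligibility checklist (Sections 4.1 and 4.4), so the text most likely to be applied at entry is the one that contains the waiver.

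The renal limit differs from the liver limits beside it. It has a stated drug-specific reason, whereas Section 5.3.1 has no matching rule for bilirubin or transaminases. At stake is a patient starting 50 mg with renal function for which the protocol's own pharmacology section points to a lower start. Fifty mg was the highest Phase I dose level (Section 2.4.1). Table 4 continues lenalidomide unchanged through grade 4 neutropenia and thrombocytopenia, so low counts would not prompt a reduction.

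**Working it through.** The plan gives no figure to reproduce on this point. The check is a comparison of texts.

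**1. Scope of the waiver.** It qualifies the limits listed after it. There are 3 (renal, bilirubin, AST/ALT). Limits exempted from the waiver: 0. So it covers 3 of 3, including the renal one.

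**2. Status of the renal limit in 5.3.1.4.** It is stated as a requirement 2 times, once as creatinine clearance for eligibility and once as eGFR plus creatinine for enrolment. Waivers attached: 0.

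**3. Which section governs.** No sentence in either section refers to the other's rule. The synopsis does not settle it. It omits the waiver for the renal limit, but also for bilirubin and AST/ALT, where 3.1.6 plainly allows one. Its silence therefore says nothing particular about the kidney.

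**4. Dose for a waived patient.** Starting doses in Tables 2 and 3: 1 (50 mg). Starting doses below 50 mg: 0. The Table 4 renal step is one level, 50 to 25 mg, and 25/50 = 0.50. It is triggered by the grade of acute kidney injury on treatment and not by an eGFR value. Stable impairment already present at entry has no stated trigger. The halving is context only; it is not a dose the protocol assigns to these patients.

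**5. Do other provisions close the gap?**

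| Provision | What it adds | Sets a renal floor? | Sets a starting dose? |
|---|---|---|---|
| Overall-PI approval (3.1.6) | Case-by-case judgement; it is the waiver mechanism itself | No | No |
| Exclusion 3.2.6: "Any condition, including laboratory abnormalities, that in the opinion of the investigator places the subject at unacceptable risk" | General investigator judgement | No | No |
| Section 5.3, pointing to the dosage and "administration schedule specified in the prescribing information" | General reference; 5.3.1.4 ties the starting-dose advice to other approved indications | No | No |
| Appendix B 3.7.3: "No exceptions to the eligibility requirements for a protocol without DFCI IRB approval will be permitted" | Possible IRB review; a waiver written into a criterion is arguably not an exception to it | No | No |

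**6. Size.** One waived patient is 1/40 = 2.5% of the evaluable patients. The documents give neither the expected number of such patients nor an exposure estimate for them on this regimen. No sample size, error rate or analysis depends on the point.

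**The case against.** The wording of the two sections is not in dispute. The other side argues weight and remedy.

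- **The evidence behind the threshold comes from a different group.** Section 5.3.1.4 cites a pharmacokinetic study in kidney disease from nonmalignant causes and refers to other indications. The waiver concerns dysfunction due to leukemia, and treatment is one 10-day course. This is fair as a caution about the size of any harm. It does not remove the conflict, because 5.3.1.4 itself carries the threshold over to this trial as an eligibility condition.
- **Independent review exists.** Appendix B, Section 3.8, requires departures from the protocol to be reported to the sponsor and on to the DFCI IRB, and requires prospective IRB approval of deviations from participating institutions. The overall PI is also the sponsor, and the Coordinating Center checks source documents for outside sites. A specific rule would often be read as overriding a general one. These points narrow the gap. But a site following 3.1.6 as written need not see itself as departing from the protocol, and none of these provisions says which section governs.
- **The cost depends on the reading.** Saying the fix loses only patients already excluded assumes that 5.3.1.4 governs. If 3.1.6 governs, eligibility becomes narrower. That stands as a qualification, although the text of 5.3.1.4 bars these patients as it is.
- **Other fixes are possible.** Section 5.3.1.4 could defer to 3.1.6, or waived patients could start at a Table 3 level. On-treatment reductions to 25 or 10 mg already occur within the same 40 patients, so the argument against mixing doses is not decisive. The documents do not show what the sponsor intended. Leaving the text unchanged is still not an answer.

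**Conclusion.** The point holds. As written, 3.1.6 allows the overall PI to admit, at the full 50 mg start, a patient whom 5.3.1.4 bars on drug-specific renal grounds. No provision resolves the conflict or gives such a patient a lower starting dose.

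It is a minor point, worth considering when the protocol is next amended. The gap is narrow, the safeguards in the table reduce it, and its effect on patients cannot be quantified from the documents. The conclusion assumes only that the waiver applies to every limit listed after it, as its wording says. The choice of remedy further assumes that the rationale in 5.3.1.4 reflects the sponsor's intent.

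**What to change.** Amend 3.1.6 so that the underlying-disease waiver applies only to the bilirubin and AST/ALT limits, and add: *The creatinine and eGFR limits may not be waived (see 5.3.1.4).* Carry the same wording into the synopsis, which now shows no waiver at all.

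This is preferable to a reduced start for waived patients. Section 2.4.1 recommends 50 mg daily for 10 days as the Phase 2 dose, and a second planned starting dose would add to the dose mixture in a 40-patient single-arm estimate. If the sponsor does want to admit leukemia-related renal impairment, 5.3.1.4 must say so and give a renal floor and a starting dose.

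The cost is one clause in 3.1.6 and the matching synopsis lines, plus the loss of any patients who would have entered through the waiver. Their number is not given, and 5.3.1.4 already bars them on its face.

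The change closes the waiver route only. Renal decline between screening (up to 21 days before treatment, Section 3.1) and Day 1, when Section 5.2 does not require eligibility to be rechecked, is a separate matter.
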